### Specific Hypothesis Testing.

**Aim 1:** GLMM for repeated measures will separately model each outcome measure as a function of treatment condition, with Level-2 effects included for best fit. Outcomes will include measures of sleep (H1a: actigraphy; self-report sleep quality; EEG), acute stress reactivity (H1b: physiological responses; subjective ratings) and cue reactivity/craving (H1c: LPP to methamphetamine images; self-report craving)

**Aim 2:** Descriptive statistics will evaluate the frequency of adverse events (AEs) and severe adverse events (SAEs) between and within conditions. Logistic regression will evaluate presence (vs. absence) of specific AEs as a function of condition.

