### Primary Hypotheses and Specific Aims:

Primary Aim 1: Determine the effects of SUVO on sleep, stress, and cue reactivity/craving

Hypothesis 1a: SUVO compared to placebo will improve sleep outcomes assessed by actigraphy (total sleep time, wake after sleep onset), self-report (Pittsburg Sleep Quality Index), and EEG (resting state alpha power);

Hypothesis 1b: SUVO compared to placebo will improve acute stress reactivity as measured by physiological responses (cold-pressor task induced cortisol and HR/BP) and subjective ratings (Visual Analog Scale; Depression Anxiety Stress Scale).

Hypothesis 1c: SUVO compared to placebo will reduce cue reactivity/craving as measured by LPP to methamphetamine images and self-report (Brief Substance Craving Scale).

Exploratory Aim 2: Evaluate the preliminary safety and side effects profile of SUVO.

**Primary outcome measures:** self-reported sleep, resting state alpha power, LPP, self-reported stress, and cortisol measured at each study visit after 1-week of SUVO, washout, and PL; total sleep time and wake after sleep onset measured nightly via actigraphy watch

**Secondary outcome measures:** methamphetamine use (TLFB and UDS) measured at each study visit after 1-week of SUVO, washout, and PL; side effects questionnaire, BDI, and CSSRS measured at each study visit after 1-week of SUVO, washout, and PL

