## Methods:

**Overall study design.** We will use a two-group cross-over design. Each group will complete three conditions, each lasting one week. 12 participants will be randomized to one of the two groups. Group one (n=6) will receive one-week placebo, one-week washout, and one-week SUVO. Group two (n=6) will receive one-week SUVO, one-week washout, and one-week placebo. During the washout period, the participants will not receive any pills. Eligibility criteria and baseline measures will be collected on Day 0 before the start of week one. Participants will come to the clinic once a week on Monday for 4 weeks. On Day 1 (Monday) of the first week, the participants will receive their medication and actigraphy watches. Each following Monday, they will complete self-report and drug use measures, as well as the laboratory tasks (cold pressor and EEG). Table 1 outlines the schedule of assessments. We will aim to enroll a total of 16 participants to complete 12, with dropouts being replaced, if possible.

**Participants, Recruitment, and Setting.** The participants will consist of non-treatment-seeking individuals meeting DSM-5 criteria for MA use disorder. All participants will be between the ages of 18-45 and fluent in English. IRB NUMBER: HSC-MS-22-0796 IRB APPROVAL DATE: 10/09/2023

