### Data Analytic Strategy:

**Overview.** Analyses will primarily rely on generalized linear modeling (GLM) for cross-sectional analyses and generalized linear mixed modeling (GLMM) for longitudinal analyses. This approach allows for various outcome distributions and multilevel data. All models will account for repeated observations with via the best-fitting structure of level-2 intercepts/slopes. We will aim to collect full data on 12 participants. Other participants who drop out or are withdrawn will be excluded from analyses, depending on how much data we are able to collect. If only a few data points are missing, generalized linear mixed modeling will natively handle missing outcome data. GLMM natively handles missing data by allowing unequally spaced observations between participants; any other issues related to missing data will be handled via explicit modeling of missingness or imputation. Analyses will be performed in R^72 via packages lme4, rstan, and brms. **Confounders:** Preliminary data analyses will inspect relationships between sample characteristics, predictors, and outcomes via GLMM. Variables that demonstrate a relationship with both the predictor and outcome in a model meet criteria for being potential confounders and yield models with and without covariate adjustment. We report the simpler model if inferences are not affected by these covariates and report both models otherwise.

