### Sample Size and Power.

The current study is primarily concerned with deriving a preliminary range of plausible effect sizes for the effect of treatment; as such, power estimates are provided here purely as due diligence. Frequentist estimates rely on G\*Power 3.1.9.7 and focus on a simplified model predicting the effect of treatment on one given normally-distributed outcome. Assuming two-sided alpha = 0.05, N = 12, 3 total measurements, a correlation among repeated measures of  $r = 0.15$ , the current proposal has 80% power to detect an effect size Cohen's  $f = 0.59$ . Notably, Bayesian inference will provide probabilistic estimates of the effect of treatment irrespective of sample size.

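### Aim 1 names no fixed period term for a two-sequence crossover, so a week 1 to week 3 shift widens the SUVO-placebo interval at 6/6 and biases the estimate if completers are unequal by sequence

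*Combined protocol and SAP*

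**What the plan says.** Under Specific Hypothesis Testing, Aim 1 is analysed as follows: "GLMM for repeated measures will separately model each outcome measure as a function of treatment condition, with Level-2 effects included for best fit". The Overview in Data Analytic Strategy describes the Level-2 effects as intercepts and slopes chosen by fit. No section names a fixed effect for period, week or visit order.

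Methods (Overall study design) sets two sequences: "Group one (n=6) will receive one-week placebo, one-week washout, and one-week SUVO", and group two has the reverse order. Washout is week 2 for everyone.

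Three other statements bear on the point:

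- Replacement (Methods): "We will aim to enroll a total of 16 participants to complete 12, with dropouts being replaced, if possible". It is not stated that a replacement takes the dropout's sequence.
- Dropouts (Data Analytic Strategy): "Other participants who drop out or are withdrawn will be excluded from analyses, depending on how much data we are able to collect".
- Covariates (Data Analytic Strategy, Confounders): "Variables that demonstrate a relationship with both the predictor and outcome in a model meet criteria for being potential confounders".

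Sample Size and Power describes the study as "primarily concerned with deriving a preliminary range of plausible effect sizes for the effect of treatment".

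**The concern.** In a two-sequence crossover, period is a design factor. If outcomes drift between week 1 and week 3 for reasons unrelated to drug, the drift adds to the SUVO-placebo difference in one sequence and subtracts from it in the other. Counterbalancing cancels this in the mean only when the sequences are equal in size. Even then the drift remains in the residual unless the model has a term for it.

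The stated terms do not supply one. A random slope on week has mean zero unless a fixed slope goes with it, and a sequence main effect does not absorb the shift. At 6/6 the confounder screen cannot admit period, because period is then unrelated to SUVO versus placebo. With unequal completers the screen has no stated threshold, so period would enter, at best, after the data are seen.

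The documents give two reasons why a drift is possible. For the watch, "On Day 1 (Monday) of the first week, the participants will receive their medication and actigraphy watches", and Potential Risks (Actigraphy) allows for discomfort while participants get used to it. Importance of Knowledge to be Gained says that taking part may itself help abstinence.

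H1a to H1c are all SUVO versus placebo, and the stated product is a range of effect sizes. The width and centring of that one interval are therefore what is at stake.

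**Working it through.** **Inputs.** N = 12, 3 measurements, r = 0.15, two-sided alpha 0.05 (Sample Size and Power); two sequences of 6 (Methods). Assumed, because the documents give no value: the week 3 minus week 1 shift p, shown from 0 to 1 outcome SD, and a true SUVO-placebo effect d = 1.16 SD for power. Compound symmetry is also assumed.

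**1. The plan's own figure.** The stated f = 0.59 at 80% power reproduces with a two-group between-factors formula: λ = N·m·f²/(1+(m−1)r) = 12·3·0.3481/1.30 = 9.64, df 1 and 10, power 0.799. It does not affect this point; only its N, m and r are used below.

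**2. Bias.** The within-person SUVO minus placebo difference has mean τ + p in group one (SUVO in week 3) and τ − p in group two. Averaged over completers, the bias is p(n1−n2)/N.

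- 6/6: 0.
- 7/5, p = 0.5: 0.5·2/12 = 0.083 SD.
- 8/4, p = 0.5: 0.5·4/12 = 0.167 SD.

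**3. Width at 6/6.** The three-condition model has residual variance 1 − 0.15 = 0.85. An unmodelled shift adds 12·2·(p/2)² = 6p² to a residual sum of squares on 22 df.

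- Without the term: half-width t(22)·√[2(0.85 + 6p²/22)/12] = 0.781, 0.788, 0.811, 0.897 at p = 0, 0.25, 0.5, 1.0.
- With the term: t(21)·√[2·0.85/12] = 0.783 throughout.

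Average half-widths from simulation (40,000 trials per cell) are slightly smaller, as expected, and show the same pattern:

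| p (SD) | Half-width, no term | Power, no term | Type I error, no term |
|---|---|---|---|
| 0 | 0.771 | 0.838 | 0.051 |
| 0.25 | 0.779 | 0.832 | 0.049 |
| 0.5 | 0.803 | 0.817 | 0.042 |
| 1.0 | 0.887 | 0.750 | 0.025 |

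With the term, half-width is 0.773 to 0.774 and power 0.834 to 0.837 at every p.

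The widening is larger if the washout visit does not share the residual. With the SUVO-placebo pair alone, the half-width is t(11)·√[(1.7 + 12p²/11)/12], which gives 0.892 at p = 0.5 and 1.061 at p = 1.0, against 0.839 with the term.

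**4. Unequal completers, simulated.**

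| Split | p (SD) | Bias | Type I error |
|---|---|---|---|
| 7/5 | 0.5 | 0.083 | 0.047 |
| 8/4 | 0.5 | 0.168 | 0.064 |
| 7/5 | 1.0 | 0.166 | 0.040 |
| 8/4 | 1.0 | 0.333 | 0.086 (coverage 0.914) |

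With the term, bias is within 0.004 and type I error is 0.047 to 0.052. At p = 0.5 and d = 1.16, power without the term depends on which sequence is larger: 0.869 or 0.759 for a 7/5 imbalance (0.83 with the term), and 0.909 or 0.688 for 8/4 (0.79 with the term).

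**5. How likely imbalance is.** Suppose 16 enrol 8/8 and 4 drop out at random (an assumption). Completers are then 6/6 with probability C(8,6)²/C(16,12) = 784/1820 = 0.43, so they are unequal with probability 0.57: 0.49 for 7/5 or 5/7, and 0.08 for 8/4 or 4/8.

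**6. Price of the term.** The variance ratio is 1/(1 − ((n1−n2)/N)²) = 1.029 at 7/5 and 1.125 at 8/4. The unadjusted variance is 2·0.85/12 = 0.1417. Setting p²((n1−n2)/N)² equal to the added variance gives break-even shifts of 0.38 SD (7/5) and 0.40 SD (8/4) for mean squared error.

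**7. Coding.** With participant effects and three conditions, adding the contrast −0.5, 0, +0.5 gives 15 columns of rank 15. A three-level week factor gives 16 columns of rank 15, because week 2 and washout coincide.

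**The case against.** The strongest reply is that the effect is small where it is likely.

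- At the planned 6/6 the estimate is unbiased, and a 0.5 SD shift costs 0.03 SD of half-width and about 0.02 of power. In the pair-only analysis, a shift below about 0.15 SD of the within-person difference (0.15·1.30 ≈ 0.20 outcome SD) leaves the interval slightly narrower without the term.
- At 7/5 the bias at p = 0.5 is about a tenth of the half-width, and type I error stays below 0.05. Inflation needs 8/4.
- Adjustment does not always help the estimate. At 8/4 and p = 0.25, mean squared error is 0.160 with the term and 0.149 without.
- The evidence for a drift is thin. Discomfort with the watch is only a possibility and concerns actigraphy alone; if confined to the first 2 of 7 nights, it moves the weekly mean by 2/7 of the nightly shift. The abstinence remark concerns methamphetamine use, a secondary outcome. Nothing specific is said for cortisol, LPP, alpha power or the stress and craving scales.
- Nightly actigraphy and the parallel Bayesian models were not simulated, and r was held at 0.15.

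All of this stands as a limit on size. It does not supply the missing term. Counterbalancing protects against bias only at 6/6, which the replacement and exclusion rules do not secure, and a covariate screen applied to observed data is not prespecification.

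**Conclusion.** The concern holds. The Aim 1 model as written has no fixed term for a week 1 to week 3 shift. At 6/6 the consequence is an interval that is too wide and a conservative test: negligible at shifts of 0.25 SD or less, about 4% wider at 0.5 SD and 15% at 1.0 SD when all three conditions share one residual. With unequal completers the estimate is biased by p(n1−n2)/N, in a direction that depends on which sequence is larger. Material type I inflation (about 0.09) appears only at 8/4 with a 1.0 SD shift. These figures rest on an assumed shift, r = 0.15, compound symmetry and, for power, d = 1.16. This is an inexpensive improvement that should be made; the omission does not undermine the trial.

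**What to change.** Prespecify the Aim 1 model as: outcome = condition (SUVO, placebo, washout) + one period contrast coded −0.5, 0, +0.5 for weeks 1, 2, 3 + sequence, with a participant random intercept. Use the same fixed terms in the frequentist and Bayesian versions. Do not enter week as a three-level factor. With week 2 coded 0, any departure in that week goes into the washout level, so no linear trend is assumed. For nightly actigraphy, give every night its week's code and keep the plan's best-fitting Level-2 structure. Take the SUVO-placebo contrast as the inference for H1a to H1c and read washout contrasts descriptively. Optionally, state that each replacement takes the dropout's sequence, which helps keep completers at 6/6.

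A random-intercept REML check of this model (20,000 trials per cell) gave a 6/6 half-width of 0.763 with the terms, against 0.762, 0.769, 0.791 and 0.867 without at p = 0, 0.25, 0.5 and 1.0.

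The cost is wording only, with no new data. If there is no shift, power goes from 0.84 to 0.83–0.84 at 6/6, to 0.83 at 7/5 and to 0.79 at 8/4. The variance is 3% higher at 7/5 and 12.5% higher at 8/4. Below a shift of about 0.4 SD, unequal completers mean accepting that extra variance in return for removing the bias.

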### Project Summary:

Methamphetamine (MA) has re-emerged as the next substance use crisis in the United States. Unlike the opioid crisis, treatment of MA use disorder is significantly more challenging without an FDA-approved medication. Most of the candidate drugs tested to date focus on modulating monoaminergic pathways, yielding limited evidence of benefit. New interventions aimed at novel biological mechanisms are needed.

Converging evidence highlights the orexin system as a promising target for addressing key mechanisms in the recovery from substance use disorders, including regulating sleep architecture, buffering hyper-arousal and stress responses, and modulating reward processing and drug-motivated behaviors. Activation of orexin (OX) receptors by psychostimulant drugs mediates arousal (OX2R) and reward (OX1R) functions and, by contrast, blockade of both receptors produces attenuation of these physiological and behavioral functions. In preclinical animal models, selective OX1R / OX2R receptor antagonism has been shown to reduce MA self-administration and MA-induced reinstatement responding. In humans with cocaine use disorder, we demonstrated that treatment with the FDA-approved dual orexin receptor antagonist suvorexant (SUVO) improved outcomes in relapse-related domains of sleep, stress, and cue reactivity. Here, we propose to expand these promising findings by examining the effects of SUVO in humans with MA use disorder, an understudied clinical population for whom there is no currently approved treatment indication.

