The primary goal of the study is to assess the effects of SUVO on physiological sleep (actigraphy, EEG) and self-reported sleep quality. We will also assess two other domains linked to the orexin system and commonly related to MA relapse including stress and cue reactivity/craving. Our overarching hypothesis is that treatment with SUVO will attenuate disruptions in sleep, stress, and cue reactivity/craving. By engaging these relapse-related target mechanisms, this work will provide critical proof-of-concept evidence for a subsequent R01. To that end, we will employ a within-subjects, two group cross-over design (N=12) and take a multimodal approach to assessing sleep, stress, and cue reactivity/craving. Participants will complete stress reactivity and electroencephalogram (EEG) laboratory tasks, self-report, and drug use measures after one week of SUVO, washout, and placebo (PL), order counterbalanced between groups. Participants will also wear an activity watch at night in order to have their sleep monitored via actigraphy.

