**Cue Reactivity/Craving (LPP).** The late positive potential (LPP) is an event-related potential component thought to reflect the motivational relevance of visual stimuli. The LPP to drug images is enhanced in drug users compared to controls, is correlated with craving, and tracks with abstinence, thus serving as an objective measure of cue reactivity/cue-induced craving. EEG will be collected on test days prior to the cold pressor task. The Picture Viewing Task will be used to elicit the LPP. Suvorexant might lead to decrease drug use through reducing reactivity toward drug cues. Therefore, the picture viewing task will provide this neural assessment of cue reactivity. In the task, the participants view images in four categories, pleasant, unpleasant, methamphetamine, and neutral. The other image categories are necessary, so that we can ensure the brain reactivity is specifically in response to drug images and not just salient images. This is a standard task used in the EEG literature and a meta-analysis shows drug users have an increased

response to drug images with a large effect size.

**Cue Reactivity/Craving (Self-Report).** The Brief Substance Craving Scale (BSCS) will be used to assess current MA craving. The BSCS will be assessed on each test day prior to laboratory tasks.

**Safety/Side Effects.** A 31-item questionnaire will be administered on each test day to assess side effects and adverse events. The Colombia Suicide Severity Rating Scale (CSSRS) and Beck's Depression Inventory (BDI) will be administered at each visit per NIH guidelines. Breath alcohol concentration will also be assessed at each visit to assess for current intoxication.

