**EEG Protocol.** On EEG days, participants will be seated comfortably in front of a monitor, fitted for the EEG cap, and the electrodes will be prepared with conductive gel. EEG will be collected using a 64-channel actiCAP electrode cap, amplified with BrainAmp MR and digitized using Brain Vision Recorder (Brain Products, Munich). The EEG machine is situated within the CNRA on the first floor of the Behavioral and Biomedical Sciences Building. Before collection, impedances will be maintained below 50 k(OHM), as suggested by the manufacturers. The sampling rate will be 250 Hz and data will be filtered with .1 Hz high-pass and 100 Hz low-pass filters. Resting State EEG. Resting state EEG will be collected prior to the Picture Viewing Task (below). We will collect resting EEG for 3 minutes with eyes opened and 3 minutes with eyes closed. Picture Viewing Task. The Picture Viewing task will be used to elicit the LPP, reflecting the motivational salience of a stimulus. During this task, participants are asked to view a slideshow of images including pleasant, unpleasant, neutral, and MA-related images. EEG Data Reduction. Data reduction will be performed with Brain Vision Analyzer 2, MATLAB, and BESA. Resting state data will be analyzed using the fast-Fourier transform. The primary outcome of interest will be alpha power (8-12Hz) although other frequencies will also be explored. Picture Viewing Task data will be segmented (200 ms pre-stimulus to 1000 ms post-stimulus) by the following conditions: unpleasant, pleasant, methamphetamine, and neutral images. The LPP will be defined as the mean amplitude between 400-800ms post stimulus over an ROI of central-parietal electrodes used in prior reports.

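### The planned H1c test of the LPP to methamphetamine images cannot separate a general suvorexant effect on picture processing from reduced drug-cue reactivity, and no planned analysis uses the control images

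*Combined protocol and SAP*

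**What the plan says.** Hypothesis 1c (Primary Hypotheses and Specific Aims) states that "SUVO compared to placebo will reduce cue reactivity/craving as measured by LPP to methamphetamine images", together with self-reported craving. Under Specific Hypothesis Testing, Aim 1 will "separately model each outcome measure as a function of treatment condition", and the outcomes for this hypothesis are "cue reactivity/craving (H1c: LPP to methamphetamine images; self-report craving". The LPP is a listed primary outcome.

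The Measures section, under Cue Reactivity/Craving (LPP), describes four picture categories. It calls the three other than methamphetamine necessary, "so that we can ensure the brain reactivity is specifically in response to drug images and not just salient images". The EEG Protocol segments the recordings "by the following conditions: unpleasant, pleasant, methamphetamine, and neutral images", and defines the LPP as a mean amplitude at 400-800 ms, not as a difference between categories.

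No section gives an image-category term, a condition-by-category interaction, a difference score or a contrast with the control pictures. The level-2 intercepts and slopes mentioned in the Data Analytic Strategy are random effects and do not supply one.

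**The concern.** The control pictures are collected to establish specificity, but the only LPP analysis in the plan ignores them. The methamphetamine-image LPP would fall if suvorexant damped the response to all pictures, or to all salient pictures, and it would fall if suvorexant damped only the response to drug cues. A test on that one category returns the same answer in each case.

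The distinction matters because of how the result is meant to be used. The Measures section gives the intended mechanism: "Suvorexant might lead to decrease drug use through reducing reactivity toward drug cues". The Project Summary adds: "By engaging these relapse-related target mechanisms, this work will provide critical proof-of-concept evidence for a subsequent R01". It also says of the arousal and reward functions of the orexin receptors that "blockade of both receptors produces attenuation of these physiological and behavioral functions". A drug that attenuates arousal could plausibly alter picture processing in general, so the rival explanation is not far-fetched. It remains an inference.

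Contrasts chosen after the data are seen would count as post hoc under the plan's Multiplicity rule. Their comparator, model and interpretation would also be open to choice at that stage.

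**Working it through.** **The plan's own figure.** Sample Size and Power gives 80% power at Cohen's f = 0.59 (two-sided alpha 0.05, N = 12, 3 measurements, correlation 0.15). The repeated-measures form for a between-groups factor with 2 groups has noncentrality f²·N·m/(1+(m−1)ρ) = 0.59²×36/1.30 = 9.64 on 1 and 10 df. Its power is 0.799, which reproduces the figure. It concerns one generic outcome and says nothing about image categories, so it does not settle this point.

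**Inputs for the illustration.**
- From the documents: n = 12, two-sided 0.05, four image categories.
- Assumed: the mixed model is simplified to a paired suvorexant-placebo comparison (11 df, critical t = 2.201). Each category's change has SD 1, with a common correlation r between category changes of 0.15, 0.3 or 0.6. The documents give no such correlation; the plan's 0.15 is the correlation among repeated measures, a different quantity. Shifts are in SDs of within-person change. The value 0.89 is the shift that gives the paired test 80% power.

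**Methamphetamine-only test.** Noncentral t with noncentrality d√12. At d = 0.3, 0.5 and 0.89 the power is 0.158, 0.353 and 0.801. What happens in the other three categories does not enter the formula, so these figures hold for a general and for a specific shift alike.

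**Contrasts.** SD of methamphetamine-minus-neutral = √(2(1−r)). SD of methamphetamine-minus-mean(pleasant, unpleasant) = √(1.5(1−r)). The 95% half-width is 2.201 × SD/√12, so for the raw effect 2.201/3.464 = 0.635.

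| r | Half-width, minus neutral | Half-width, minus mean(pleasant, unpleasant) |
|---|---|---|
| 0.15 | 0.83 | 0.72 |
| 0.3 | 0.75 | 0.65 |
| 0.6 | 0.57 | 0.49 |

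The contrasts are less precise than the raw effect when 2(1−r) > 1 (r below 0.5) and when 1.5(1−r) > 1 (r below about 0.33), respectively.

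**How often the confidence intervals lie wholly on the reduction side** (200,000 simulated trials per cell, shift 0.89 SD; three values are for r = 0.15, 0.3, 0.6):

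| True pattern | Minus neutral | Both contrasts |
|---|---|---|
| Equal shift in all four categories | 2.5% at each r | 0.5% at each r |
| Neutral shifts half as much as the other three | 19%, 22%, 35% | 1.7%, 1.8%, 2.1% |
| Methamphetamine only | 58%, 66%, 88% | 48%, 58%, 85% |

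The middle row shows why the neutral contrast alone is not enough. A fall shared by all salient pictures passes it too often. The contrast with pleasant and unpleasant pictures removes that fall.

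**Model form.** The four category means in a visit come from one EEG session. In a joint model of the 12×3×4 = 144 values with a participant intercept only, the average standard error of the neutral contrast was 0.398, 0.391 and 0.371, against true values of 0.377, 0.340 and 0.259. That is 6%, 15% and 43% too large. A visit-within-participant intercept corrects this but is not sufficient. If participants also differ stably in their category responses, with variance k times the residual variance, and the model omits that effect, the pooled residual variance is (33(1+3k) + 66)/99 = 1 + k times the true one. The standard error is then too large by √(1+k): 22%, 41% and 73% at k = 0.5, 1 and 2. A contrast score formed within each visit cancels the shared session level, and comparing conditions within participant cancels stable category differences.

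**The case against.** The strongest reply is that the test answers its hypothesis. H1c and Aim 1 both name the LPP to methamphetamine images, and neither claims specificity. This stands. A reader might infer that a significant result under a general shift would be a false positive for H1c. It would not be; it misleads only if reported as drug-specific.

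A second reply is that the Measures section calls the image categories necessary, not any particular comparison, and may only be explaining why the task is valid. The first half is correct: a treatment-by-category contrast is this review's proposal, not an unmet promise in the text. But the stated purpose is to rule out a response to salience in general, and that can be done only by comparing categories.

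Third, the harm is conjectural. A reader might infer that suvorexant is known to alter the LPP to all pictures. The documents report no suvorexant effect on the LPP of any kind, and every shift and correlation above is assumed.

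Fourth, resting EEG, recorded just before the picture task, and self-reported methamphetamine craving bear on a general-arousal explanation. They help with interpretation but do not compare picture categories within the same task.

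Finally, this is a pilot of 12 that seeks a range of plausible effect sizes. That argues for reporting the contrasts as estimates with intervals, not for leaving them out.

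**Conclusion.** The gap is real and limited. The control images are collected for specificity, and no planned analysis uses them. The named test responds identically to a general and to a drug-specific reduction: 80% rejection at 0.89 SD in either case. Requiring both contrast intervals to lie on the reduction side separates the two, at 0.5% against 48% to 85%. That there is no planned contrast is certain from the text. The size of the consequence is not: it rests on a paired simplification, equal SDs, and assumed shifts and category correlations. The documents do not support saying that the H1c test is wrong, that control data are missing, or that a general shift will occur. The change is worth making because the LPP is a primary outcome and the remedy needs only analysis wording.

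**What to change.** Leave the H1c test as it is. Prespecify two supporting estimates: the suvorexant-placebo difference in (a) methamphetamine-minus-neutral LPP and (b) methamphetamine-minus-mean(pleasant, unpleasant) LPP.

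- Compute each as a within-participant contrast score per visit and analyse it with the same condition model as the other outcomes. If a joint condition-by-category mixed model is preferred, include both visit-within-participant and participant-by-category random effects, since omitting either misstates the contrast's standard error.
- Report both contrasts with 95% confidence and credible intervals. Label them supporting estimates, not additional primary tests, so that they do not lengthen the list tested at an uncorrected 0.05.
- State the wording rule in advance: an LPP reduction is described as drug-cue-specific only if the intervals for both contrasts lie wholly on the reduction side. Otherwise, report a reduction in the LPP to methamphetamine images that may be general.

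The cost is some SAP text and analysis time, with no new data or visits. The downside is precision. With weakly correlated category changes the contrasts are less precise than the raw effect, and the rule would leave a true methamphetamine-only effect of 0.89 SD unconfirmed in about 52%, 42% and 15% of trials at assumed correlations of 0.15, 0.3 and 0.6 (100% minus 48%, 58% and 85%). The report should say that failing the rule is not evidence of a general effect.
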